## Direct Benefits to Subjects

*Describe only benefits to individual subjects that are likely to accrue during the study itself. Do not include subject compensation or treatment to be provided at the end of the study, as these do not figure into the IRB's risk benefit considerations. Do not describe diagnostic and evaluation components unless subjects receive clinical feedback. Do not describe the anticipated scientific benefits of the research. Some studies offer no direct benefit to subjects.*

There are no benefits to individual participants, other than the knowledge they may gain about options for protection against HIV, other STIs, and pregnancy, possible access to PrEP, and the potential for attitudinal change that will facilitate better safer-sex decision making. The information gained from this study will help design an intervention to promote uptake and sustained use of an efficacious HIV prevention tool, which could potentially help address the extraordinary vulnerability of young, South African women to HIV infection.

---

Therefore, we believe the risks are reasonable in relation to the anticipated benefits.

**COVID-19 sub-study:** There are no direct benefits to individual study participants and the study is not designed for their benefit. Participants may, however, benefit by gaining access to resources and services that they have difficulty obtaining were as a consequence of COVIC-19 lockdowns.

## A Gender-enhanced PrEP-Exposure Prophylaxis Information-Motivational Workshop for Young South African Women – Data analysis plan 24 june 2022

### From the original proposal

#### 3.3.9.3 Statistical analysis

**Aim 3a.** Workshops: Compare participants (N=100) randomized to Gender-Enhanced or Information-Only Workshops on undergoing PrEP clinical assessment (primary outcome); uptake of PrEP if eligible, and 3-month PrEP retention (secondary outcomes) and hypothesized mediators (risk perception, gender barriers, self-efficacy, outcome expectancies, PrEP-stigma, attitudes, peer norms, information) post-intervention and at 3-months. To compare the **primary and secondary outcomes** across the two workshop conditions, we will use generalized linear models (GLM) with a logit link function and the method of generalized estimating equations (GEE) to account for the effect of clustering within workshop and clustering within recruitment chain. Intervention condition will be the primary predictor. We will adjust for any substantial baseline differences by group on age. To assess if being a PHA, i.e., talking to other women about HIV prevention serves as an additional intervention dose, a secondary analysis will include a variable for whether the woman served as a PHA and recruited other workshop attendees (yes/no).

For the hypothesized mediators, all of which are summary measures from multi-item scales, we will use GLM with an identity link function and GEE (to account for clustering effects) to compare the mean difference between the two intervention groups from post-test to pre-test, and from 3-month follow-up to post-test, to determine if there is an increase, decrease, or no change over time (difference of difference analysis), adjusting for age if necessary.

Accompanying these tests will be point and interval estimates for parameters of interest. Since our aim is not to estimate proportions (or means) from a theoretically representative population, we will *not* use respondent-driven sampling (RDS) weights; our aim is only to account for the greater similarities of individuals by recruitment and intervention-delivery clusters.

**Aim 3b.** Peer-driven recruitment: 1) Assess acceptability and feasibility of PDR using pre-specified performance (process) criteria for acceptance and recruitment (on average  $\geq 50\%$  of attendees become PHAs and  $\geq 2$  recruits/PHA attend a workshop); and 2) Evaluate reach of PDR (percent who score high on a new HIV risk tool (10); percent who never tested and never attended family planning. We will estimate these simple proportions from the tracking data and from the pre-workshop assessments.

Power Considerations. The primary goal for this pilot work is to collect preliminary data regarding feasibility, acceptability and target outcomes for the proposed intervention. In line with guidelines from PA-17-166: *Formative and Pilot Intervention Research for Prevention and Treatment*, which caution against using pilot studies (where the sample size is of necessity small) to obtain an estimate of an effect size, we will use these pilot data to rule out unusually large or small true effects through standard 95% confidence interval procedures. We will confirm extrinsic effect sizes are contained within our confidence intervals from the pilot. We will examine the distribution of each variable, and calculate summary statistics by intervention condition. We will estimate key intervention parameters with sample means and proportions together with two-sided 95% confidence intervals, and test the primary null hypotheses at the traditional two-sided level  $\alpha=.05$  (simulation of the subsequent RCT). For planning the RCT, we will also consider one-sided 90% confidence limits for mission-critical *design parameters* such as standard deviations and reference group endpoint rates and proportions in the conservative direction. This is because we intend to plan sample size for the RCT so that power will be “excellent” (at least 80% power) for the clinically relevant effect size to be specified. This strategy will make proper allowance for the limited sample size of the pilot study with its consequent uncertainties, and still yield appropriate sample sizes for the RCT. “Mission-critical” parameters include proportions for dichotomous endpoints (uptake of PrEP clinical assessment, uptake of PrEP yes/no); means and standard deviations for continuous potential mediators of outcome (e.g. gender barriers, PrEP-stigma). Large sample sizes are not required to locate these parameters approximately, but adequately, for planning the subsequent trial, whereas testing the study hypothesis in the pilot

will generally not have sufficient statistical power. Estimation of mission-critical design parameters with point and confidence interval estimates will be considered highly important; continuous outcome measures make it feasible to detect promising effect effects even in small samples. For the continuous measures, means and standard deviations (sd) will be estimated. For approximately normally distributed variables, an upper one-sided 90% confidence limit for the sd,  $\sigma_u$ , will be constructed from  $\sigma_u = s \chi^2_{v,10}^{1/2}$ , where s is the sample sd and  $\chi^2_{v,10}$  is the upper 10th percentile of the chi-squared distribution with v degrees of freedom. For approximately log-normally distributed variables, a logarithmic transformation will be applied to achieve approximate symmetry and normality. For the dichotomous variables (such as the primary and secondary outcomes, or the PDR performance criteria), exact binomial methods will be employed for the CIs for proportions. As an example, the width of the exact 95% confidence interval around a point estimate of 40% (e.g., percent women who score high-risk) would be 30%-50% with 100 participants.

While testing the primary null hypothesis is not the primary goal for this pilot study, if we assume the proportion of women who undergo PrEP clinical assessment in the information-only group ranges from 20% to 50%, with total sample size of 100 participants we are still able to declare a difference of 33 to 36 percentage points as statistically significant at 0.05 level with power of 80% if the within recruitment chain and within intervention-delivery group correlation coefficient is no greater than 0.1. As an illustration of how this can be used for planning the large randomized trial, suppose in this pilot study, proportion of participants take PrEP risk screening is 85% and 50% for Gender-Enhanced workshop and Information-Only Workshop respectively while the minimally clinically relevant improvement, on extrinsic grounds, is an improvement of 15 percentage points. Then, N=240 per group would be required in the RCT. The above plan will allow us to assess feasibility and acceptability, estimate factors influencing intervention parameters, and examine the range of possible effect sizes for our primary outcome. Therefore, the information collected from this pilot study should put us in an excellent position to conduct a future full-scale RCT.

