Subsequent recruitment. Subsequent PHAs (Waves 2-4) will be drawn from workshop attendees (who do not have to agree to be PHAs), and their numbers will be supplemented if needed using Wave 1 recruitment procedures. At the end of a workshop (or, for IA participants, after viewing the online materials), study staff will invite all participants to become PHAs and to reach out to their network members to help them prevent HIV infection. PHAs will invite network members to participate in the activity (GE or IA) they, themselves, participated in (and will inform them that brief assessments are included). We will repeat this process three more times, for a total of four recruitment “waves” (see Table below). We expect that the initial PHAs (n=16, Wave 1) will refer 28 workshop attendees. Of these 28, we expect at least 50% will agree to be PHAs (Wave 2). These 14 will average two referrals (n=28) who are eligible and participate. We expect half of participants to agree to be PHAs (Wave 3), through a total of four waves. If we fail to enroll 14 new PHAs from the pool of attendees, we will add new recruits, as for the initial seeds. We expect each wave will take approximately two months. To attain a target **98 100** participants attending and completing Waves 2 through 4, we anticipate that we may need to enroll up to 120 women.

Peer-driven recruitment waves and follow-up N = 100 <del>98</del> 100	Wave 1 (seeds)	Wave 2	Wave 3	Wave 4 (if need ed)	
Study Months					
Wave 1: Seeds randomized (1:1) to attend GE or IA condition  Workshop (WS)	16				
Wave 2: Recruitees who participate attend WSs		28 14			
WS Attendees who become PHAs					
Wave 3: Recruitees who participate attend WSs			28 14		
WS attendees who become PHAs					
Wave 4: Recruitees who participate attend WSs				28	
WS Attendees who become PHAs					
Total Attendees/wave (N= 98 <del>100</del> )	16	28	28	28 <del>30</del>	
Follow-up interviews		16	28	28	28

[figure not shown]

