## Data Analysis

Workshops: Compare women randomized to the virtual group-interactive workshop with those randomized to individually-accessed links to a PrEP promotional video and PrEP information on the **primary outcome of having an individual discussion with the study nurse about the possibility of taking up PrEP; undergoing HIV self-testing guided by the study nurse (either in-person at the GHRU office or via telehealth visit) (secondary outcome); if eligible for PrEP, initiating PrEP (secondary outcome)**, and, for all women, changes in hypothesized mediators (information, risk perception, gender barriers, outcome beliefs, PrEP-stigma, peer norms) post-intervention and at 3-month follow-up.)

To compare the **primary and secondary outcomes** across the two workshop conditions, we will use generalized linear models (GLM) with a logit link function and the method of generalized estimating equations (GEE) to account for the effect of clustering within recruitment chain. The logit link function is appropriate because the primary and secondary outcomes are dichotomous and characterized as yes/no if achieved at any time over the course of the study by the time of the 3-month follow-up interview. Intervention condition (Gender-Enhanced or Individual Access) is the primary predictor. Although the original data analysis plan also specified accounting for clustering by workshop group attended, we will not account for clustering by workshop group because women in the IA condition received the intervention as individuals rather than as groups.

We will adjust for any substantial baseline differences by condition on age. We will also adjust for any substantial differences by other demographic and behavioral characteristics, such as education level, whether attending school, has a primary partner, sexual risk behaviors (to be defined), relationship power, reported intimate partner violence if these factors differ substantially by condition at baseline and are also associated with the outcome (i.e., meet the conditions of confounding).

To assess if being a PHA, i.e., talking to other women about HIV prevention serves as an additional intervention dose, a secondary analysis will include a variable for whether the woman served as a PHA and recruited other workshop attendees (yes/no).

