**Mediators.** “Other outcomes” include those measures designed to tap constructs that are hypothesized in our theoretical model to be mediators, i.e., on the pathway between the intervention and the outcome. These are factors that we believe influence the outcome (women considering PrEP for themselves) and that if changed by the intervention will lead to an increase in this outcome. We want to know if these factors are influenced by the gender-enhanced intervention and help explain (mediate) any changes in the main outcomes. These hypothesized mediators, most of which are summary measures from multi-item scales, include PrEP information, perceived risk for HIV, perceived effectiveness of PrEP, positive outcomes of taking PrEP, gendered HIV prevention barriers related to partner disclosure, PrEP-related stigma, normative beliefs, medication beliefs. Please see the related document entitled “Table of pilot study measures 2022 June 22.” for descriptions.

An additional variable—stage of change for adopting PrEP--was added when we revised the study. This will also be considered a mediator, although at 3month followup, the last option of this measure is “I am taking PrEP”. This is the indicator for the outcome of initiating PrEP.

For the mediators, we will first test if the intervention had any effect on them, using generalized linear models (GLM) with an identity link function and GEE (to account for clustering effects) to compare the mean difference between the two intervention groups from post-test to pre-test, and from 3-month follow-up to post-test, to determine if there is an increase, decrease, or no change over time (difference of difference analysis), adjusting for age and other confounders if necessary. As per [name]: the model is of the form:

$E(Y|X,T1,T2)=\text{constant}+b1*X+b2*T1+b3*T2+b4*X*T1+b5*X*T2$ , where X is the intervention indicator, T1 and T2 are post-intervention and 3-month FU indicator respectively. The regression coefficient b4 represents the group difference in change of the outcome Y (i.e., the potential mediators) from pre- to

post-intervention, however, it is b5-b4 (NOT b5) that represents the group difference in change of Y from post-intervention to 3-month FU.

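### The 3-month mediator contrasts can be biased if survey loss depends on earlier scores and differs by arm, because the planned GEE states neither a within-woman correlation nor a method for missing surveys

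*SAP*

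**What the plan says.** The operative text is the Mediators paragraph of the SAP's Data Analysis section. It tests the intervention effect on each mediator "using generalized linear models (GLM) with an identity link function and GEE (to account for clustering effects". The mean model has an arm indicator X, two time indicators ("T1 and T2 are post-intervention and 3-month FU indicator respectively") and their products with X, with coefficients b1 to b5. The contrasts of interest are b4 (pre to post) and b5-b4 (post to 3 months).

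Section 3.3.9.3, carried over from the original proposal, gives the same method ("we will use GLM with an identity link function and GEE (to account for clustering effects"). For the primary and secondary outcomes it planned "to account for the effect of clustering within workshop and clustering within recruitment chain". The current section narrows this to "to account for the effect of clustering within recruitment chain" and explains: "we will not account for clustering by workshop group because women in the IA condition received the intervention as individuals". The mediator paragraph itself names no cluster unit, so recruitment chain is what remains.

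Neither document states a working correlation, a within-woman covariance, a missing-data assumption, a method for absent surveys, or an expected 3-month loss rate. The nearest figure is the Protocol's enrolment allowance for the pilot: "we anticipate that we may need to enroll up to 120 women".

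**The concern.** All three assessments are self-administered through a link sent to the woman's phone, so some 3-month surveys will probably be missing. GE women join a 90-minute live group, whereas IA women receive links. Unequal loss is therefore plausible, although nothing in the documents shows it.

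A GEE fit uses the surveys that were returned. Under working independence, the 3-month contrasts are differences of available-case means. Under a single exchangeable correlation per chain, the strong correlation within a woman is averaged with the weak correlation between women. In both cases a missing 3-month survey is hardly informed by that woman's own post-test score. If low scorers drop out more often from IA, the IA women who remain look better and the GE effect at 3 months is understated.

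Two later uses depend on these estimates. Mediators found to be altered by the intervention go into the mechanism models (Data Analysis, final mediator step). Mediator means and SDs are also among the design parameters for the full trial (Power Considerations).

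**Working it through.** The documents give no precision, power or loss figure for the mediator models, so there is no planned figure to reproduce.

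**Inputs from the documents.** About 100 women, 16 seeds and hence about 16 chains, three assessments, and intra-chain correlation of at most 0.1. The enrolment allowance implies 1 - 100/120 = 16.7%, but it covers attending and completing Waves 2 to 4 and is not a 3-month loss rate.

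**Assumed inputs.** Scores in SD units with higher being favourable, within-woman correlation ρ = 0.5 to 0.7, and odds of loss (OR) 2 to 3 times higher per SD lower post-test score. Loss by arm is GE 17% / IA 17%, 10% / 24%, or 5% / 29%.

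**1. Dilution under exchangeable-by-chain correlation.** Seven women with three surveys each give 21 records and 21 × 20 / 2 = 210 pairs. Only 7 × 3 = 21 pairs (10%) are within a woman. With ρ = 0.6 and chain correlation 0.1, the pooled value is 0.10 × 0.6 + 0.90 × 0.1 = 0.15. A woman's earlier scores then carry little weight.

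**2. Large-sample bias of available-case means.** Let Z be the post-test score standardised within arm, let logit P(loss) = a - ln(OR) × Z with a set to give loss rate π, and let δ(π) = E[Z | retained]. The retained 3-month mean is shifted by ρδ(π). Because b4 uses only pre and post surveys,

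bias(b5-b4) = bias(b5) = ρ × [δ(π_GE) - δ(π_IA)].

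| OR | δ(5%) | δ(10%) | δ(17%) | δ(24%) | δ(29%) |
|---|---|---|---|---|---|
| 2 | 0.0338 | 0.0662 | 0.1103 | 0.1534 | 0.1838 |
| 3 | 0.0510 | 0.0978 | 0.1597 | 0.2195 | 0.2616 |

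- 17% / 17%: the shifts cancel and the bias is 0.
- 10% / 24%: from 0.5 × (0.0662 - 0.1534) = -0.044 to 0.7 × (0.0978 - 0.2195) = -0.085 SD.
- 5% / 29%: from 0.5 × (0.0338 - 0.1838) = -0.075 to 0.7 × (0.0510 - 0.2616) = -0.147 SD. Against an assumed effect of 0.40 SD, the largest value is 0.147/0.40 = 37%.
- With a weaker link (OR 1.5) the two unequal cases give about -0.03 to -0.07 SD.

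**3. Simulation at pilot size.** 16 chains, N = 100, chain correlation 0.05, ρ = 0.5, OR about 2, true b5 = 0.40, 600 runs per case, Monte Carlo error 0.009. The table shows the mean estimate of b5.

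| Loss GE / IA | GEE independence | GEE exchangeable by chain | Mixed model, woman and chain effects |
|---|---|---|---|
| 17% / 17% | 0.403 | 0.403 | 0.399 |
| 10% / 24% | 0.362 | 0.368 | 0.401 |
| 5% / 29% | 0.334 | 0.343 | 0.404 |

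**4. The SAP's own contrast, and the limits of the problem.** 16 chains of 7 women, chain correlation 0.1, within-woman correlation 0.6 or decaying (0.7/0.7/0.4), true b4 = 0.5 and b5 = 0.4, overall loss 15 to 19%, 1,500 runs, Monte Carlo error about 0.005. Bias in b5-b4:

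| Loss depends on | GEE (independence or exchangeable) | Woman-level covariance plus chain |
|---|---|---|
| Arm only | -0.004 to 0.006 | -0.004 to 0.005 |
| Pre-test score, same rule in both arms | -0.008 to 0.004 | -0.006 to 0.004 |
| Post-test score, same rule in both arms | -0.045 to -0.055 | -0.007 to 0.005 |
| Post-test score, one arm only | -0.108 to -0.144 | -0.006 to 0.004 |
| Post-test score, opposite rules | -0.209 to -0.291 | -0.005 to 0.004 |
| Unseen 3-month score, one arm only | -0.197 to -0.216 | -0.122 |

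The last row is for the equal-correlation case only. In the third row the arms already differ at post-test, so one rule produces unequal loss. The empirical SE of b5-b4 was 0.16 to 0.21 SD across methods.

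**5. Which mixed model.** In 240 runs of 40 chains of 8 women with post-test-driven loss in one arm, a mixed model with a chain intercept alone had bias -0.106, against -0.107 for exchangeable GEE. With decaying correlation, an equal-correlation woman effect left up to -0.024. At pilot size (16 chains, 96 women, true b5-b4 = 0, unequal score-related loss), REML with unstructured within-woman covariance plus a chain intercept converged and stayed within about 0.02 SD of truth, with a slightly smaller SD. Chain GEE was shifted by about -0.02 to -0.14 SD.

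**The case against.** The strongest reply is that the plan is silent on this point, which is different from choosing a wrong method. The mediator paragraph names neither the cluster unit nor the working correlation, and a working correlation that captured the woman level would use her earlier scores. That is fair. The defect is that the SAP as written permits, and by default leads to, a nearly available-case analysis at 3 months.

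Several stronger inferences are tempting but not supported:

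- A reader might infer that the GEE is unbiased only when loss is unrelated to earlier scores. It is not so: with equal 17% loss tied to the post-test score, or with loss tied to the pre-test score by one rule in both arms, the bias was within Monte Carlo error.
- A reader might infer that any mixed model cures the problem. A chain-only model does not. With loss driven by the unseen 3-month score, even the woman-level model kept -0.122 of about -0.2 SD.
- A reader might take the 120-to-100 allowance as a planned 3-month loss of 17%. The Protocol's wave table plans follow-up interviews of 16, 28, 28 and 28, equal to attendees. The unequal splits are assumptions.
- A reader might infer that the bias decides which mechanisms are tested. A mediator can qualify as altered through b4, which 3-month loss does not touch.

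It also stands that the bias is smaller than the sampling error, that the mediators are not the primary outcome, and that the SAP says a pilot of this size will generally lack power for hypothesis tests.

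**Conclusion.** The point holds in a limited form. The SAP leaves the working correlation and the missing-survey method unspecified for scores repeated on the same woman. With a simple chain-level correlation, b5-b4 and b5 can be biased when loss depends on earlier scores and differs by arm. Under the assumed inputs the size is roughly -0.02 to -0.15 SD, against a sampling SE of about 0.2 SD. Loss tied to the score in one arm only, or in opposite directions, can give more. b4 is unaffected by 3-month loss.

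The sizes rest on the assumed correlation, loss odds and loss rates by arm, none of which the documents give. This is a worthwhile correction to a secondary analysis and does not touch the primary result. The gain is a 3-month contrast that is valid under a weaker, stated assumption.

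**What to change.** Keep the Data Analysis mean model and b1 to b5 exactly. For the scale-score mediators:

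- Fit it as a linear mixed model by REML, with an unstructured covariance over the three assessments within woman and a random intercept for recruitment chain.
- Include every woman with at least one assessment.
- State that the analysis is valid under missing-at-random loss and a correctly specified model.
- Keep the GEE as a sensitivity analysis, with its cluster unit and working correlation named.
- Add a sensitivity analysis for loss that depends on the unseen 3-month score.
- Report 3-month loss by arm and by post-test score. This would show whether the risk arose.

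The cost is SAP wording and different model code. No new data are needed, and under the identity link the coefficients keep their meaning. The downside is that the model assumes approximate normality and a correct covariance, so it suits the multi-item scales better than the ordinal stage-of-change item, which needs its own stated analysis. Because the effect-modifier section, updated in December 2022, already shows subgroup counts, the change should be entered as a dated amendment.

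### Requiring the extrinsic effect to lie inside the pilot's 95% confidence interval is the wrong check for a minimally relevant improvement, because an effect well above it counts as not contained

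*SAP*

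**What the plan says.** The relevant text is in the SAP, section 3.3.9.3, under Power Considerations.

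- **Purpose of the interval:** "we will use these pilot data to rule out unusually large or small true effects through standard 95% confidence interval procedures".
- **The check:** "We will confirm extrinsic effect sizes are contained within our confidence intervals from the pilot". No direction, effect scale or consequence of non-containment is given.
- **The extrinsic effect:** it is not yet fixed; the RCT is to have "at least 80% power) for the clinically relevant effect size to be specified". The only value offered comes in an illustration, where "the minimally clinically relevant improvement, on extrinsic grounds, is an improvement of 15 percentage points".
- **The pilot's precision:** if "the proportion of women who undergo PrEP clinical assessment in the information-only group ranges from 20% to 50" per cent, then "with total sample size of 100 participants we are still able to declare a difference of 33 to 36 percentage points as statistically significant" with 80% power, provided the within-chain and within-group correlation is at most 0.1.
- **The between-arm model:** the later Data Analysis section uses "generalized linear models (GLM) with a logit link function" and GEE, clustered on recruitment chain. The intervals described for dichotomous variables are exact binomial intervals for proportions.

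The December 2020 revisions and the Data Analysis section neither restate nor withdraw the containment check.

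**The concern.** A minimally relevant improvement is a floor, and an effect larger than the floor is good news. Two-sided containment treats it otherwise: once the whole interval sits above the floor, the floor is no longer contained. At the other end, an interval from about 50 women per arm is wide enough that an intervention with no effect will often contain a moderate target. If both happen often, the check can rank a useless intervention above a strong one.

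What is at stake is the interpretation of the pilot effect. Read literally, the report could say that the target was confirmed when the data are compatible with no effect, and not confirmed when the data favour a much larger effect.

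There is also a smaller gap. The target is an absolute difference, while the specified model gives an odds ratio, and no interval for the between-arm difference is named.

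**Working it through.** **Inputs.** Target 15 points, reference rate 20-50%, illustrative result 85% vs 50%, and N=100: all from the SAP, Power Considerations. About 50 per arm: the Protocol, Conduct of workshops, expects roughly 50 of roughly 100 women in the gender-enhanced arm. The SAP gives no cluster size, so the design effect (DE) is an assumption.

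**Reproducing the SAP's figure and choosing DE.** With ICC 0.1 and cluster size m, DE = 1 + (m − 1) × 0.1. Solving for the difference detectable with 80% power at two-sided 0.05 and 50/DE per arm, over the stated reference range:

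- DE 1.0: 26.0-27.6 points
- DE 1.6 (m = 7): 32.8-34.7 points
- DE 1.7 (m = 8): 33.7-35.8 points

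The stated 33-36 points is recovered to about one point with m of 7 to 8. DE 1.6 is therefore close to what the SAP appears to have assumed. Results are shown for DE 1.0 and 1.6.

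**Containment probability.** For reference rate pc and true difference d, with pt = pc + d:

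SE = √{[pc(1 − pc) + pt(1 − pt)] × DE / 50}

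P(contains 15 points) = Φ((0.15 − d)/SE + 1.96) − Φ((0.15 − d)/SE − 1.96)

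Worked case, pc = 0.50 and DE 1:

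- d = 0: SE = √(0.50/50) = 0.100; Φ(3.46) − Φ(−0.46) = 0.677.
- d = 0.35: SE = √((0.25 + 0.1275)/50) = 0.0869; Φ(−0.34) − Φ(−4.26) = 0.366, so not contained in 63.4%.

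| Reference rate | Null: contained, DE 1 | Null: contained, DE 1.6 | +35 points: not contained, DE 1 | +35 points: not contained, DE 1.6 |
|---|---|---|---|---|
| 20% | 53.4% | 68.3% | 60.1% | 41.7% |
| 30% | 62.7% | 74.7% | 57.1% | 39.4% |
| 40% | 66.6% | 77.3% | 58.0% | 40.1% |
| 50% | 67.7% | 78.0% | 63.4% | 44.4% |

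In every row, and at both design effects, the null effect is contained more often than the 35-point effect. At 30% and DE 1.6, for example, the figures are 74.7% against 100 − 39.4 = 60.6%. A true 15-point effect is contained 95% of the time by construction.

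**Check on the approximation.** Exact enumeration of two binomials of 50, unclustered, gives null containment of 53-69% (Wald interval) or 53-67% (Newcombe). Non-containment at +35 points is 59-63% (Wald) or 51-60% (Newcombe).

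**The SAP's own example, 85% vs 50%.** The interval is 35 ± 1.96 × 8.69 × √DE points:

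- DE 1.0: 18.0 to 52.0, which excludes 15
- DE 1.4: 14.8 to 55.2, which just contains 15
- DE 1.6: 13.5 to 56.5, which contains 15

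**Dependence on the target.** For a null effect, containment of a 10-point target is 76-83% at DE 1. For a 20-point target it is 30-48% at DE 1 and 49-65% at DE 1.6.

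**Directional alternative.** If the target is contradicted only when the upper limit is below 15 points, the chance of meeting the check is 1 − Φ((0.15 − d)/SE − 1.96). Under the null this is 53.4-67.7% at DE 1 and 68.4-78.1% at DE 1.6, within 0.1 point of the two-sided figures. At a true 15 points it is 97.5%. At a true 35 points it is above 99.9%.

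**Scale.** Fifteen points corresponds to odds ratios of 2.15, 1.91, 1.83 and 1.86 at reference rates of 20%, 30%, 40% and 50%, so no single odds ratio represents the target.

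**The case against.** The strongest reply is that containment is not a pass/fail rule. The SAP attaches no decision to it and warns against taking an effect size from a pilot. RCT planning there rests on an extrinsic effect and on one-sided 90% limits for design parameters. In the illustration the pilot shows 35 points, yet the RCT is sized for 15; the quoted 240 per group matches 50% vs 65%, at 90% power with continuity correction. Nothing is treated as failed. This stands. A reader might infer that the check drives the RCT sample size or works as a go/no-go gate, and the documents support neither.

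Five further points narrow the concern.

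- **The target is illustrative.** A reader might infer that the check passes most null interventions whatever the target. At 20 points without clustering it does not.
- **The SAP's example.** A reader might infer that the 85% vs 50% result fails the check. It does so only without clustering; from a design effect of about 1.4 the interval contains 15, and the SAP plans a clustered analysis.
- **Discrimination.** The check is not uninformative between no effect and the target: 53-78% containment against 95%.
- **Scale.** The SAP promises point and interval estimates, and a risk difference follows from a logit GEE by routine post-estimation. The gap is missing detail; the model is not wrong.
- **Status of the text.** The sentence sits in the part carried over from the original proposal, written for a different comparator and outcome definition. It has not been withdrawn, so this lowers its weight without removing it.

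None of this answers the directional fault: for a floor, falling outside on the high side should not count against the target.

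**Conclusion.** The concern holds in limited form. Two-sided containment is the wrong check for a minimally relevant improvement. With a 15-point target, 50 per arm and a 20-50% reference rate, a true 35-point effect goes uncontained in about 57-63% of pilots unclustered and 39-44% at a design effect of 1.6. A null effect is contained in about 53-68% and 68-78% respectively. A null effect is therefore more likely to meet the check than the SAP's own illustrative effect.

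These figures rest on the illustrative 15 points, a normal approximation (supported by exact enumeration in the unclustered case) and an assumed design effect. The consequence is confined to how the pilot effect is interpreted and reported.

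The high null pass rate is mainly a result of 50 women per arm. The SAP already acknowledges that the pilot will generally lack power for the hypothesis test. No rewording of the check removes that, which is why the word confirm is misleading here.

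**What to change.** 1. Name the estimand for this comparison: the between-arm risk difference, standardised from the logit GEE, with a 95% CI robust to clustering by recruitment chain.
2. Replace containment with a directional reading: the pilot argues against the extrinsic target only if the upper 95% limit is below it. An interval wholly above the target does not count against it.
3. State the extrinsic value, or the range under consideration, before the between-arm results are read.
4. Add a sentence on operating characteristics: the directional reading stops strong effects from failing, but a null effect would still meet it in about 53-78% of pilots at 15 points. Meeting the check is to be reported as the target not being ruled out, and never as the target being confirmed.

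The cost is a few lines of SAP text and one standard post-estimation step. No new data, design change or change to the RCT sizing method is needed.
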